## IV lidocaine v. hydromorphone for acute abdominal pain. A randomized trial. Version date 07112018

administration

- 3) Patient preference for the medication they received.
- 4) Need for medication to treat associated symptoms such as anti-nausea medication or an anti-histamine

### Safety endpoints

- 1) Frequency of development of any new symptom after administration of the investigational medication
- 2) Frequency of requirement of naloxone
- 3) Frequency of a change in the disposition of the patient attributable to investigational medication
- 4) Frequency of missed diagnosis, defined as an unplanned return visit to the ED resulting in hospital admission

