## IV lidocaine v. hydromorphone for acute abdominal pain. A randomized trial. Version date 07112018

arms of the trial, research subjects and research personnel will be asked, at the time of ED discharge, to guess which medications were administered.

**Stratification.** Subjects will be stratified by study site (Moses or Einstein) and diagnosis (presumptive diagnosis of kidney stones versus non-kidney stone presumptive diagnosis). The rationale for stratification based on presumptive diagnosis of kidney stones is two-fold: 1) kidney stones represent a large subset of abdominal pain diagnoses; 2) kidney stones may be more likely to respond to IV lidocaine than other causes of abdominal pain

**Details of protocol.** Patients who present to our ED with acute abdominal pain will be referred by the attending emergency physician to the research staff for enrollment. Because of the severity of pain, only those who can appropriately make an informed decision about participating will be enrolled (those who cannot will be screened and excluded). Eligibility will be ascertained by research associates and verified by the site investigator. An EKG will be performed and interpreted by the attending physician. A point-of-care urine pregnancy test will be performed. Capacity to consent to participate in this study will be assessed by the attending emergency physician and documented. Masked medication will be obtained from the pharmacy. The research associate will perform a baseline pain assessment. Prior to the administration of any medication, patients will be placed on a cardiac monitor with telemetry where they will have continuous measurement of their heart rate and oxygenation. Blood pressure will be measured every 15 minutes for the first hour. The ED nurse will administer the research medication as described above. Research associates will perform an assessment of pain and adverse events every 30 minutes. Use of off-protocol medication to treat pain or associated symptoms will be recorded. Seven days after enrollment, patients will be contacted by telephone to determine satisfaction with the medication, course of pain subsequent to the ED visit, and occurrence of any adverse events.

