### Measures

- 1) Pain intensity will be measured using a verbal numerical scale of which 0 represents no pain and 10 represents the worst pain imaginable
- 2) Medication preference. Preference for a specific medication is a highly patient centered outcome, in which an individual determines for herself the benefit of a particular drug versus the adverse effects experienced. We will include in this study a measure that has been used in multiple ED-based trials—"The next time you come to the ER for treatment of abdominal pain, do you want to receive the same medication again?" Patients will be asked to choose among the following responses: "Yes," "No," or "Not sure"
- 3) Side effects. We will use the following question: "Did you have any new symptoms that began only after you got the study medication?" An affirmative response will be followed by an open-ended question eliciting details.

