### Risks/Benefits

Hydromorphone is commonly used in US EDs for treatment of acute abdominal pain. Intravenous lidocaine is an emerging medication for acute severe pain with some data to support its use. Regardless of results, this study will likely have a national impact. Study subjects will benefit by receiving a medication that is likely to improve their pain. In addition to breach of confidentiality, which is unlikely, and inconvenience to the subject, which will undoubtedly occur, it is likely that subjects will experience adverse medication effects. For the most part, these are nuisance events. All the medications can cause drowsiness, which may be functionally impairing. Opioids such as hydromorphone can cause respiratory depression and hypotension. Lidocaine can very rarely cause hemodynamically significant cardiac arrhythmias or seizures.

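### The serious harms that the plan names for each drug are not prespecified as safety endpoints compared by arm, so the safety half of the aim is only partly answered

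*Combined protocol and SAP*

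**What the plan says.** The aim, stated just before Methods, is to determine both the efficacy and the safety of IV lidocaine relative to IV hydromorphone.

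Safety endpoints lists four items. The first is broad: "Frequency of development of any new symptom after administration of the investigational medication". The second concerns use of one antidote: "Frequency of requirement of naloxone". The third counts changes in disposition that are put down to the study drug. The fourth counts missed diagnoses, recognised by an unscheduled ED return that ends in admission.

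Under Measures, side effects are elicited by asking the patient "Did you have any new symptoms that began only after you got the study medication", with an open-ended follow-up after a yes.

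Risks/Benefits names the harms of concern. For the comparator: "Opioids such as hydromorphone can cause respiratory depression and hypotension". For the test drug: "Lidocaine can very rarely cause hemodynamically significant cardiac arrhythmias or seizures".

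Details of protocol states that "patients will be placed on a cardiac monitor with telemetry where they will have continuous measurement of their heart rate and oxygenation". It adds blood pressure every 15 minutes during the first hour, a check of pain and adverse events every 30 minutes, and a telephone call at 7 days that asks about adverse events. A committee reviews adverse events monthly. Analysis states that dichotomous values will be given as proportions with 95% CI.

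**The concern.** The plan identifies four serious harms, two for each drug, and watches the physiological signals for most of them. It does not define any of the four, set a recording threshold, or say that they will be tabulated by arm. The safety result would rest mainly on how many patients report a new symptom.

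That measure has two weaknesses. A fall in blood pressure, a drop in oxygenation or a rhythm disturbance that the patient does not feel is not a symptom, so the question cannot pick it up. And as a frequency of any symptom, it gives a seizure the same weight as the transient dizziness or paresthesia described in Background.

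The naloxone item is the one endpoint that points to a specific toxicity, and that toxicity is opioid. Background says that lidocaine side effects in pain patients resolved by stopping the drug, slowing the infusion, or observation. None of these responses is counted. Analysis keeps patients whose infusion was not completed, yet a stop for an adverse event is not an endpoint.

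At stake is whether the report can state, for each named harm, how many patients in each arm had it. Without prespecification, the choice of which events to report, and how to group them, is left until the data are known.

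**Working it through.** **Step 1. Named harms against endpoints** (Risks/Benefits, Details of protocol, Safety endpoints).

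| Named harm | Drug | Monitoring described | Own endpoint |
|---|---|---|---|
| Respiratory depression | hydromorphone | continuous oxygenation | none; naloxone use is a partial proxy |
| Hypotension | hydromorphone | blood pressure every 15 min, first hour | none |
| Arrhythmia | lidocaine | cardiac monitor with telemetry | none |
| Seizure | lidocaine | nothing specific | none |

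None of the four harms has its own endpoint. Of the four endpoints, one (naloxone) concerns a specific toxicity, and none is specific to lidocaine. The other three apply to either drug.

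**Step 2. Which arm the omission affects.** Two of the omitted harms are tied to hydromorphone and two to lidocaine. Leaving out the first pair spares hydromorphone; leaving out the second spares lidocaine. The documents give no event rates, so no net direction follows.

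**Step 3. Arm size.** Inputs from Sample size calculation: difference 1.3, SD 2.8, alpha 0.05 (taken as two-sided), power 0.80.

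n per arm = 2 × (1.960 + 0.842)² × 2.8² / 1.3² = 2 × 7.849 × 7.84 / 1.69 = 72.8, rounded up to 73. This reproduces the plan's figure.

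Total = 2 × 73 × 1.05 = 153.3, rounded up to 154, or 77 per arm. This also reproduces.

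**Step 4. What per-arm counts could show at 77 per arm.**
- Exact two-sided 95% upper limit with no events: 1 − 0.025^(1/77) = 4.7%. With 73 per arm it is 1 − 0.025^(1/73) = 4.9%.
- Chance of seeing at least one event in an arm, 1 − (1 − p)^77, at assumed true rates p:

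| p (assumed) | 0.1% | 0.5% | 1% | 2% | 5% |
|---|---|---|---|---|---|
| P(at least one) | 7% | 32% | 54% | 79% | 98% |

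- Fisher's exact test, k of 77 against 0 of 77: k = 5 gives p = 0.058; k = 6 gives p = 0.028. A formal difference therefore needs at least 6 against 0, that is 6/77 = 7.8% against 0%.

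For rare harms the counts would be descriptive.

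**The case against.** The strongest case on the other side is that serious events already have routes into the results. One that changes disposition and is judged attributable to the study drug counts under the third endpoint in either arm. Adverse events are checked every 30 minutes and again at 7 days, the open-ended follow-up would distinguish a reported seizure from dizziness, treatment of associated symptoms is a secondary outcome, and a committee reviews adverse events monthly. With 77 per arm, extra rows for rare events would rarely separate the arms.

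Much of this stands. It would be wrong to infer that the named harms are not analysed at all; they are not prespecified as separate endpoints. But the third endpoint catches only events that alter disposition and pass an attribution judgement. The follow-up details have no stated scheme for classification or grading. The adverse event checks and committee review do not commit the trial to a comparison by arm. Rarity limits what can be tested, but 0 of 77 with its upper limit still tells the reader something, and the plan already promises intervals for proportions.

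A reader might also infer that naloxone can be charged only to hydromorphone and that the whole safety comparison is therefore tilted toward lidocaine. The documents do not support this. Beyond one hour, further treatment is left to the clinician, and Secondary efficacy outcomes foresees off-protocol opioids. Analysis keeps such patients in their arm, and the naloxone endpoint has no attribution clause. Naloxone after a rescue opioid would therefore count in the lidocaine arm. It would still reflect opioid toxicity, so the lack of a lidocaine counterpart remains. Hypotension, a hydromorphone risk, has no endpoint either.

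Finally, Details of protocol describes measurement at the bedside. It does not say that the monitor readings are entered as study data, so the fix cannot be assumed to be free.

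**Conclusion.** The concern holds as a gap in prespecification that affects both arms. All four harms named in Risks/Benefits lack a definition and a planned comparison by arm, the general endpoint cannot detect symptomless events or separate serious from minor ones, and the only toxicity-specific endpoint concerns opioids. The safety comparison is incomplete; bias in favour of lidocaine is not shown.

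The primary efficacy analysis is untouched. The gap is worth closing because relative safety is part of the aim, but the gain is in description: an upper limit of 4.7% when no events are seen, and no formal difference short of 6 against 0. These figures assume that all 77 patients per arm start the study drug. The event rates used above are assumptions, since the documents give none.

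**What to change.** Add to Safety endpoints, for each arm, the number and proportion of patients with 95% CI, labelled descriptive, for:
- arrhythmia
- seizure
- hypotension
- respiratory depression or desaturation
- infusion stopped early for an adverse event

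Keep naloxone and pair it with any treatment given for study-drug toxicity, so that the item can register toxicity from either drug. The investigators set the recording definitions and thresholds before enrolment, and the plan states which readings are entered as study data.

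The cost is some added REDCap fields and data entry, including capture of relevant monitor findings. Sample size, treatment and procedures stay as they are.

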### Sample size calculation.

Based on previous work, we anticipate a mean improvement in 0-10 pain score of 4.9 and a standard deviation of 2.8. Using a between-group difference of 1.3 as a minimum clinically significant difference, an alpha = 0.05 and a beta = 0.20, we determined the need for 73 patients in each group. We will enroll 105% of this N in anticipation of protocol violations and missing data, thus leaving us with a sample size of 154 patients. With 73 patients in each arm, the sample size is sufficiently robust that the ttest can be used even if the data are not normally distributed (central limit theorem).

### Analysis.

Baseline characteristics will be reported as mean (SD), median (IQR), or n/N (%), as appropriate. The primary outcome, improvement in 0-10 pain score between baseline and one hour will be reported as mean (95%CI) for each group. The between-group difference in mean improvement in 0-10 pain score will be calculated with 95%CI. If this 95%CI does not cross zero, the results will be considered statistically significantly different. All dichotomous values will be reported as proportions with 95%CI. For formal statistical testing, we will use the ttest.

We will use an intention to treat analysis. Once an investigational medication is initiated, the patient will be included in the analysis, regardless of whether or not the patient completed the medication infusion and regardless of whether or not the patient requests off-protocol analgesic medication.

**Data collection and processing.** Data acquisition will be performed using REDCap (Research Electronic Data Capture), a secure, web-based application designed specifically to support data capture for research studies. The REDCap project (<http://project-redcap.org/>) is an international project, with more than 70 institutional partners from CTSA and GCRC funded institutions. Paper consent documents will be maintained in locked research cabinets.

**Data monitoring committee and interim analysis.** This committee will be headed by [name], PhD, an epidemiologist and include [name], MD, the director of the Moses ED. The committee will meet every month with the PI to 1) monitor adverse events and develop strategies to minimize these; and, 2) monitor recruitment and enrollment. Because our goal is to report the results with sufficient precision to influence clinical practice, we will not perform an interim efficacy analysis.

**Registration.** The study will be registered at <http://www.clinicaltrials.gov>.

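### The primary analysis is an unadjusted t-test on change scores; adjusting for baseline pain, site and kidney-stone stratum costs almost nothing and could narrow the deciding 95% CI

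*Combined protocol and SAP*

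**What the plan says.** The Analysis section of the combined protocol and SAP defines the primary comparison: "The between-group difference in mean improvement in 0-10 pain score will be calculated with 95%CI". The decision rule follows: "If this 95%CI does not cross zero, the results will be considered statistically significantly different". The test is named once: "For formal statistical testing, we will use the ttest". The sample size section plans for the same test and argues that "the sample size is sufficiently robust that the ttest can be used even if the data are not normally distributed". No covariate, regression model or stratified analysis is named anywhere in the documents.

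The design, however, supplies covariates. Under Stratification: "Subjects will be stratified by study site (Moses or Einstein) and diagnosis" (presumptive kidney stone or not). The reasons given are that "kidney stones represent a large subset of abdominal pain diagnoses" and that "kidney stones may be more likely to respond to IV lidocaine than other causes of abdominal pain". Under Details of protocol, a research associate scores pain before any study drug is given.

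**The concern.** Two features of the planned analysis can make the interval wider than it needs to be.

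- **Strata.** Stratified blocks keep the arms balanced on site and diagnosis, so differences between strata largely drop out of the treatment contrast. The unadjusted standard error still counts that variation. If the strata predict improvement, the t-test is conservative and its CI too wide.
- **Baseline pain.** Taking a change score fixes the coefficient of baseline pain at 1. That is fully efficient only if improvement is unrelated to baseline pain.

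What is at stake is precision, not validity. The 95% CI is the decision rule, so an interval wider than necessary can leave a real difference undeclared. The Data monitoring paragraph also gives precision as a goal: "Because our goal is to report the results with sufficient precision to influence clinical practice". That sentence is there to explain why there is no interim efficacy analysis, so it supports the point only indirectly.

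**Working it through.** **Inputs from the documents (Sample size calculation, Analysis).** Difference 1.3 points; SD of improvement 2.8; alpha 0.05, taken as two-sided because the rule is a 95% CI against zero; power 80%; 73 per arm.

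**Plan's own figure.** n per arm = 2 × [2.8 × (1.960 + 0.842) / 1.3]² = 72.8, rounded up to 73. Then 146 × 1.05 = 153.3, rounded up to 154. Both reproduce.

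**Planned t-test at 73 per arm.** SE = 2.8 × √(2/73) = 0.463. With 144 df the critical t is 1.9766, so the half-width is 1.9766 × 0.463 = 0.916. Noncentral-t power for 1.3 points is 79.6%.

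**Adjusted model.** Three covariates leave 141 df (critical t 1.9769). Let R² be the share of variance in improvement that they explain; it is assumed, because the documents do not give it. Then SE = 2.8 × √[(1 − R²) × (2/73) × f], where f allows for chance imbalance in the covariates:

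- (a) f = 1: imbalance ignored, slightly optimistic.
- (b) f = 1 + 1/142: imbalance in baseline pain only. This is the most realistic, since blocking largely balances the strata.
- (c) f = 1 + 3/140: all three covariates treated as unbalanced, an upper bound on the cost.

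| R² | power (a) | power (b) | power (c) | half-width (a) | half-width (c) |
|---|---|---|---|---|---|
| 0 | 79.6% | 79.3% | 78.7% | 0.916 | 0.926 |
| 0.02 | 80.4% | 80.1% | 79.5% | 0.907 | 0.917 |
| 0.05 | 81.6% | 81.3% | 80.7% | 0.893 | 0.903 |
| 0.10 | 83.6% | 83.3% | 82.8% | 0.869 | 0.878 |
| 0.20 | 87.6% | 87.4% | 86.9% | 0.82 | 0.828 |

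Break-even under (c) is R² of about 0.021. Simulation with all three covariates (15,000 replicates) gave, at R² = 0, power 78.5% adjusted v 79.0% unadjusted and half-width 0.918 v 0.914; at R² = 0.20, adjusted power was 86.9%.

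**Baseline pain alone.** Let k be baseline SD divided by follow-up SD, and ρ their correlation. Then R² = (k² − ρk)² / [k²(k² + 1 − 2ρk)]. Holding the change SD at 2.8, the implied baseline SD is 2.8k / √(k² + 1 − 2ρk). Power is by method (a).

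| k | ρ | R² | implied baseline SD | power |
|---|---|---|---|---|
| 0.5 | 0.5 | 0 | 1.6 | no gain |
| 0.5 | 0.3 | 0.042 | 1.4 | 81.2% |
| 0.75 | 0.5 | 0.077 | 2.3 | 82.6% |
| 1 | 0.5 | 0.25 | 2.8 | 89.6% |

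**Strata alone.** Simulation with stratified blocks of four, N = 146, total SD 2.8 and an assumed 25% stones (40,000 null and 20,000 alternative replicates; Monte Carlo SE of type I error 0.11 percentage points). Each cell shows unadjusted v adjusted.

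| Assumed stone, site effect (points) | type I error | power |
|---|---|---|
| 0, 0 | 5.1% v 5.1% | not reported |
| 1, 0.5 | 4.7% v 5.1% | 80.1% v 81.0% |
| 1.5, 0.5 | 4.1% v 4.9% | 80.4% v 82.2% |
| 2, 1 | 3.7% v 5.0% | 80.9% v 84.2% |

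In the last row the SE falls from 0.463 to 0.432.

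**The case against.** The strongest reply is that nothing is broken. Under randomisation the t-test is unbiased, its type I error stays at or below about 5%, it has the planned power, and the sample size and analysis sections agree with each other. The choice is between two valid estimators, and the benefit of one rests wholly on unstated quantities. All of that stands, and it is why this is a recommended improvement and not a required repair.

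The larger gains also deserve less weight. Entry requires that an intravenous opioid already be planned, which may compress baseline pain, whereas the 89.6% case needs a baseline SD of 2.8 on a 0–10 scale. A 2-point stone effect exceeds the plan's own 1.3-point minimum clinically significant difference. The stated stone rationale concerns a different response to lidocaine, that is, effect modification; it does not show that stones predict improvement in both arms. The gain may therefore be small or nil.

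What the reply does not overturn is the asymmetry: at worst a loss of under one point of power, against roughly 3 to 8 points gained if 10–20% of variance is explained. Nor can the choice safely wait, because an adjusted model picked after unblinding would be open to the charge of selection.

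**Conclusion.** The concern holds. The plan specifies an unadjusted t-test on change scores and ignores both stratification factors. Adjustment costs at most about 1% of CI width (0.916 to 0.926) and 0.9 points of power if the covariates explain nothing. At 10–20% of variance explained, it narrows the half-width from 0.92 to between about 0.88 and 0.82 and raises power from 79.6% to about 83–87%. At 2–5% explained the gain is between nil and about two points.

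These figures rest on the plan's SD of 2.8 and difference of 1.3, 73 evaluable patients per arm, and assumed values for the explained variance, the baseline SD and correlation, the stone share and the stratum effects. The direction of the argument is firm; the size of the benefit cannot be fixed from the documents.

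**What to change.** In the Analysis section, make the primary analysis a linear model (ANCOVA) of improvement at the primary time point on arm, baseline 0–10 pain, site and presumptive kidney-stone stratum. Use the adjusted difference and its 95% CI as the decision rule, and keep the t-test as a sensitivity analysis. Fix this before unblinding.

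Two inconsistencies must be reconciled before the model can be written. The primary outcome is set at 90 minutes under Outcomes but at one hour under Analysis. The second site is called Weiler under Study setting but Einstein under Stratification.

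Optionally, report the stone and non-stone differences with 95% CIs and an arm-by-diagnosis term, labelled exploratory, and state how imprecise they are. At an assumed 25% stones (18.25 and 54.75 per arm), the half-widths are about 1.9 and 1.06 points. The interaction SE is 2.8 × √(2/18.25 + 2/54.75) = 1.07, a half-width of about 2.1. Power for a 1.3-point interaction is about 23% (17–28% at 15–40% stones), and 80% power needs an interaction of about 3.0 points.

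Cost: analysis wording and three degrees of freedom (144 to 141). All covariates are already collected, so no extra patients or procedures are needed.

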## Background

Intravenous opioids are commonly used to treat acute abdominal pain in US emergency departments (ED). These medications are highly efficacious and, when used in a monitored setting such as the ED, extremely safe. Use of opioids has fallen out of favor because of a spike in opioid-related overdose deaths throughout the US. While use of opioids in the ED is unlikely to contribute to outpatient opioid deaths, minimizing the use of opioids in the ED will contribute to an opioid free culture, in which opioids are used only when absolutely necessary. A variety of different types of medications can be used in lieu of opioids. One such medication, intravenous lidocaine, has been used extensively in various arenas including the operating room, where it is an evidence-based preventive of post-operative pain, and the cardiac care unit, where it historically had been used to prevent arrhythmias. Some data suggest that it may be efficacious for acute abdominal pain as well.

Intravenous lidocaine has long been used to treat pain. In publications dating back to 1980, intravenous lidocaine has been shown to be an effective treatment for neuropathic pain (2). In the post-operative setting, intravenous lidocaine decreased pain and decreased the need for opiates (3-7). More recently, emergency medicine investigators in Iran, demonstrated that intravenous lidocaine decreased pain associated with renal colic and limb ischemia (9-11). An ED-based study in the US showed comparable efficacy between morphine and intravenous lidocaine when used for acute abdominal pain (12).

Over the years, intravenous lidocaine has been used for a variety of indications including arrhythmia prophylaxis in patients with acute coronary syndromes. Known side effects of intravenous lidocaine range from transient neurological symptoms (dizziness, paresthesias), to cardiac dysrhythmias and seizure. To date, no deaths have been attributed to its use for treating pain and the only documented significant complication was due to an unintentional overdose where a patient received ten times the normal dose (2, 3, 8). All reported side effects in pain patients have been transient and resolve by stopping the drug, decreasing the infusion rate, or by observation alone. Thus, intravenous lidocaine is an emerging medication for safe and rapid relief of pain, has no known addictive properties, and creates a potential for a pain practice paradigm shift in the United States.

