### Outcomes.

Primary efficacy outcome. The primary endpoint for this study will be improvement in improvement in 0-10 pain score between medication administration and 90 minutes later.

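### Does the plan need a rule for reading a primary 95% CI that includes both zero and a 1.3-point loss with lidocaine?

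*Combined protocol and SAP*

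**What the plan says.** The aim, at the end of the Background, is to determine the relative efficacy and safety of IV lidocaine against IV hydromorphone. The Methods call the trial a comparative effectiveness study. No section states a non-inferiority or equivalence hypothesis or margin.

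Under Analysis, the between-group difference in mean improvement is to be given with its 95% CI, and the formal test is the t test. The decision rule is "If this 95%CI does not cross zero, the results will be considered statistically significantly different". Nothing further is said about an interval that does include zero.

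The figure of 1.3 points appears only under Sample size calculation: "Using a between-group difference of 1.3 as a minimum clinically significant difference".

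Three other statements bear on how a null result might be used:

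- Risks/Benefits: "Regardless of results, this study will likely have a national impact".
- Data monitoring committee and interim analysis: "Because our goal is to report the results with sufficient precision to influence clinical practice, we will not perform an interim efficacy analysis".
- Background, on an earlier trial: "An ED-based study in the US showed comparable efficacy between morphine and intravenous lidocaine when used for acute abdominal pain".

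**The concern.** The comparator is described as the putative standard of care, and the Background wants less opioid use in the ED. In that setting a non-significant difference is easily taken as support for substitution. A difference test cannot give that support, because an interval that includes zero may also include a loss that the plan itself regards as clinically important. The decision rule covers only intervals that exclude zero, and 1.3 is never brought back in the Analysis. The statements about impact, precision and comparable efficacy can be read as signs that a null result will be put to use.

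At stake would be the wording of the conclusion: with no rule fixed before unblinding, an inconclusive result could be presented as equivalence.

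**Working it through.** **Inputs.** SD of improvement 2.8, difference 1.3, alpha 0.05 and beta 0.20 (Sample size calculation); 1:1 allocation (Investigational medications); t test and 95% CI (Analysis).

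**The plan's own figure.** n per arm = 2 × (1.960 + 0.842)² × 2.8² / 1.3² = 72.8, so 73. A one-sided test would need 58, so the calculation is two-sided and matches the 95% CI rule. The exact t calculation gives 73.8, and power at 73 per arm is 79.6%. Inflation: 146 × 1.05 = 153.3, so 154. The sample size stands.

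**Width of the interval.** SE = 2.8 × √(2/73) = 0.4635. Half-width = t(0.975; 144) × SE = 0.916.

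**When the interval holds both values.** Let d be lidocaine minus hydromorphone. The interval contains 0 if d ≥ −0.916 (for d below zero) and contains −1.3 if d ≤ −1.3 + 0.916 = −0.384. So d must lie between −0.916 and −0.384.

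**How often.** For a true loss L the probability is Φ((−0.384 + L)/0.4635) − Φ((−0.916 + L)/0.4635):

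| True loss with lidocaine | Probability |
|---|---|
| 0 | 18.0% |
| 0.325 | 34.8% |
| 0.65 | 43.4% |
| 0.975 | 34.8% |
| 1.3 | 18.0% |

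Simulation with an estimated SD gives 17.9% to 43.0%. With all 77 per arm analysed the range is about 16% to 41%. With assumed SDs of 2.5 and 3.1 at 73 per arm it is 10% to 31% and 26% to 52%. If lidocaine is truly better by 0.3 or 0.5, the probability falls to 6.6% or 2.7%.

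**What a reader would see.** Take an observed loss of 0.65, the middle of the zone. The reported interval runs from a loss of 0.65 + 0.916 = 1.57 to a gain of 0.916 − 0.65 = 0.27. It visibly contains both zero and 1.3. The estimate, the interval and the benchmark are all planned or published in advance, so nothing is hidden.

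**Whether the plan claims more than its test supports.**

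- The precision statement gives the reason for having no interim efficacy analysis. It does not speak of null results.
- The impact statement is a general remark on the study's importance in a section on risks and benefits.
- The comparable-efficacy phrase describes an earlier trial against morphine, not a conclusion planned for this one.

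None of the three commits the sponsor to reading a null result as equivalence.

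**Whether a rule for this zone would settle the matter.** Suppose such intervals had to be called inconclusive. At a true difference of 0, 100% − 2 × 2.4% = 95.2% of trials are null. Of all trials, 18.0% fall in the zone, which leaves 95.2% − 18.0% = 77.2% null and still without a stated reading. At a true loss of 0.3 the split is 34% in the zone and 57% outside it; at 0.5 it is 41% and 40%. The mirror case, zero together with a 1.3-point gain, is equally likely at a true difference of 0 (18.0%) and would not be covered. Barring the word comparable in this zone alone could even suggest that it is allowed for the other null results.

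**The case for a change.** The strongest case for the concern is that reporting an interval does not bind the authors' conclusion, whereas a sentence written before unblinding does. If the true loss is 1.3, 20.4% of trials are null, and 88% of those have an interval that still contains 1.3. A sentence would cost nothing in sample size or alpha.

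Much of this stands as description. The plan is silent on the clinical reading of an interval that includes zero, the probabilities are right on the plan's own inputs, and a null result here would not by itself establish comparable efficacy. A claim that an important loss had been excluded would need more than this plan offers. It would need a justified margin and an analysis that deals with rescue, since patients are analysed "regardless of whether or not the patient requests off-protocol analgesic medication". Power to exclude a 1.3-point loss is about 80% only at a true difference of zero, and falls to 57% at a true loss of 0.3 and 40% at 0.5. But the plan makes no such claim, so these are requirements for a different aim. An overstated conclusion would be a fault of the eventual report, and the published interval would expose it.

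One nearby matter is real but separate. Under Outcomes the primary endpoint is "improvement in 0-10 pain score between medication administration and 90 minutes later", while under Analysis it is "improvement in 0-10 pain score between baseline and one hour". Those passages must be reconciled, but the conflict does not alter the arithmetic here or create a need for an interpretation rule.

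**Conclusion.** The concern does not hold. For the question asked, the plan has a sound estimate, a two-sided 95% CI, a correct decision rule that agrees with the t test, and a sample size that reproduces at 73 per arm and 154 in total. An interval that holds both zero and a 1.3-point loss would occur in 18% to 43% of trials if the true loss lies between 0 and 1.3. That rests on SD 2.8, 73 evaluable patients per arm and a t interval; the documents do not say where in that range, or outside it, the truth lies. The figure describes the ordinary uncertainty of a trial with 80% power at 1.3 and does not reveal a fault. No computed result would change. A sentence on interpretation is a reporting preference, and one confined to this zone would leave most null results unread if the drugs are truly equal (77% of all trials).
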